Prescription medications of relevant comedications including anticoagulation therapy, antiarrhythmic drugs, and other medications (see Annex 2, Table 13) in the individual 4 quarters before the index quarter (pre-index period) will be assessed.

Table 2 – Definition of covariates

Variable	Category	Operational definition
Age	continuous	Age in the index quarter.
Gender	categorical	Sex on the index date.

Insurance status	categorical	
Insurance status on the index date:
 
 • regular insurance • retired • family insured • unknown
Number of hospitalizations	continuous	Total number of hospitalizations, independent of admission diagnosis, during the baseline period.
No of unique medications	continuous	Number of unique pharmaceutical substances (unique ATC 5 Codes) per patient received during the baseline period, based on the prescriptions documented in the database.
Interactions with co-medications	categorical	
In order to determine whether patients were concurrently treated with other medication interacting with Rivaroxaban or Phenprocoumon, it will be assessed whether patients received any of the relevant substances in the 90 days before the Index date.
 
For a list of medications with interaction potential see Table 12.

CHA ₂ DS ₂ -VASc Score	continuous	
The CHA₂DS₂-VASc score will be derived by assigning one point each for hypertension, diabetes mellitus, and heart failure, vascular disease (peripheral artery disease, myocardial infarction, aortic plaque), age 65-74 years, female sex and two points for age 75 years or older, previous stroke or transient ischemic attack (TIA), with a total possible score of nine [Trappe 2012].
 
Ambulatory verified as well as primary and secondary hospital discharge diagnoses within in the 12 months before the index date will be used to assess the CHA₂DS₂-VASc score.
 
For a complete list of all ICD-10 codes which will be used to form the CHA₂DS₂-VASc score please refer to Annex 2. Tables.

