
CHADS₂ Score
	
continuous
	
The CHADS₂ Score will be derived by assigning one point each for hypertension, heart failure, age 75 years and older, diabetes mellitus. A preliminary stroke/TIA will be assigned two points, with a total possible score of six [Trappe 2012].
 
Ambulatory verified as well as primary and secondary hospital discharge diagnoses within in the 12 months before the Index date will be used to assess the CHADS₂ score.
 
For a complete list of all ICD-10 codes which will be used to form the CHADS₂ score please refer t to Annex 2. Tables.

Charlson Comorbidity Index (CCI)
	
continuous
	
The Charlson Comorbidity Index (CCI) will be used to weigh comorbidities in the baseline period depending on their severity.
 
Ambulatory verified as well as primary and secondary hospital discharge diagnoses within the 12 months before the index date will be used to build the CCI score. A list of included conditions and their assigned weights can be found in Annex 2. Tables.
 
Please consider the following publications for further information regarding the applied methodology:
 

Comorbidity Index (modified Charlson Comorbidity Index)	continuous	
In order to avoid a high degree of correlation between some covariates a separate Comorbidity Index was defined, which includes only disease categories which are not already measured by the HAS BLED score.
 
This modified Comorbidity Index contains all Charlson disease categories except hypertension, congestive heart failure, cerebrovascular disease, mild, moderate or severe liver disease and moderate or severe renal disease.

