Bleeding history (modified HAS BLED Score)	continuous	
The HAS-BLED score is derived for each patient in the baseline period by assigning one point and summing the score across the following conditions: hypertension, renal disease, cirrhosis, and stroke, major bleeding event, age 65 and older, use of non-steroidal anti-inflammatory drug, intake of antiplatelet agents, alcohol abuse.
 
Since the HRI database does not contain any laboratory parameters, the international normalized ratio (INR) will not be included in the HAS-BLED score.
 
For a complete list of all ICD codes which will be used to form the HAS-BLED score please refer to Annex 2. Tables.

Myocardial infarction (MI)	categorical	
Ambulatory verified diagnoses in the four quarters prior to the index quarter as well as primary and secondary hospital discharge diagnoses within the 365 days before or on the index date will be used to assess whether patients suffered from a previous myocardial infarction. MI will be defined using the ICD-10 GM code I21.* and I22.*.

Chronic renal insufficiency	categorical	
Ambulatory verified diagnoses in the four quarters prior to the index quarter as well as primary and secondary hospital discharge diagnoses within the 365 days before or on the index date will be used assess whether patients suffered from a chronic renal insufficiency. Chronic renal insufficiency will be defined using the ICD-10 GM code N18.*.

Chronic renal insufficiency stage I	categorical	Ambulatory verified diagnoses in the four quarters prior to the index quarter as well as primary and secondary hospital discharge diagnoses within the 365 days before or on the index date will be used assess whether patients suffered from a chronic renal insufficiency, stage I. Chronic renal insufficiency, stage I will be defined using the ICD-10 GM code N18.1.
Chronic renal insufficiency stage II	categorical	Ambulatory verified diagnoses in the four quarters prior to the index quarter as well as primary and secondary hospital discharge diagnoses within the 365 days before or on the index date will be used assess whether patients suffered from a chronic renal insufficiency, stage I. Chronic renal insufficiency, stage II will be defined using the ICD-10 GM code N18.2.

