Hypertension	categorical	Ambulatory verified diagnoses in the four quarters prior to the index quarter as well as primary and secondary hospital discharge diagnoses within the 365 days before or on the index date will be used assess whether patients suffered from hypertension. Hypertension will be defined using the ICD-10 GM code I10.*.
Congestive heart failure	categorical	Ambulatory verified diagnoses in the four quarters prior to the index quarter as well as primary and secondary hospital discharge diagnoses within the 365 days before or on the index date will be used assess whether patients suffered from congestive heart failure. Congestive heart failure will be defined using the ICD-10 GM code I50.*.

Atherosclerosis of arteries of extremities	categorical	Ambulatory verified diagnoses in the four quarters prior to the index quarter as well as primary and secondary hospital discharge diagnoses within the 365 days before or on the index date will be used assess whether patients suffered from peripheral vascular disease. Peripheral vascular disease will be defined using the ICD-10 GM code I70.2.
Ischemic stroke or TIA during baseline	categorical	Ambulatory verified diagnoses in the four quarters prior to the index quarter as well as primary and secondary hospital discharge diagnoses within the 365 days before or on the index date will be used assess whether patients suffered from ischemic stroke or TIA. Ischemic stroke or TIA will be defined using the ICD-10 GM code I63, I64, G45.9 and G45.8.
Coronary heart disease	categorical	Ambulatory verified diagnoses in the four quarters prior to the index quarter as well as primary and secondary hospital discharge diagnoses within the 365 days before or on the index date will be used assess whether patients suffered from coronary heart disease. Coronary heart disease will be defined using the ICD-10 GM code I20*(angina pectoris), I24.*(other acute ischemic heart diseases) and I25* (chronic ischaemic heart disease).
Liver disease		
Mild liver disease	categorical	Ambulatory verified diagnosis in the four quarters prior to the index quarter as well as primary and secondary hospital discharge diagnoses within the 365 days before or on the index date will be used assess whether patients suffered from a mild liver disease. Mild liver disease will be defined using the ICD-10 GM codes according to the Charlson Comorbidity Index (Table 8).

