Almost 80% of the insured individuals in the database are observable for the entire available observation period of up to six years. Thus, analyses including comparatively large study populations with a long observation period are possible.

The HRI database is updated on an annual basis, guaranteeing studies with the most recent data. As the database has an administrative time lag until completion and clean up for all areas of health care of about 9 months, most data will be available for the preceding year, mid of the following calendar year.

Structure of the database

The database refers to different health care sectors such as the inpatient, outpatient, and pharmacy sector, and provides detailed information on the resource use and cost of these services. It includes amongst others, the following data:

- **Patient Demographics:** Record of continuous enrollment for a unique set of demographics (e.g. insurance begin and end, age, gender, date of death, which relates to the beginning of the quarter) for each individual. In addition, the insurance status (e.g. retired, family insurance), region of residence, and the type of occupation are included.
- **Inpatient Care:** Contains records that summarize hospital admission information such as ICD-10-GM (German Modification of the ICD-10 codes) codes in primary or secondary position, and Diagnosis Related Groups (DRG) code. It also includes the length of stay (date of hospital admission and end of hospital stay) and all performed procedures and surgeries (OPS). Furthermore, discharge diagnosis code or death in hospital, and costs of inpatient stay are included.
- **Outpatient Care:** Contains services that were rendered in a physician's office in the quarter in which the diagnosis (ICD-10-GM code) was documented. In addition, the procedures performed (e.g. laboratory, radiology echocardiography) by EBM codes and day of performance. Furthermore, the type of specialist that documented the diagnosis and performed the procedure (e.g. cardiologist, general practitioner) and costs of outpatient care are available.

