- **Pharmaceutical Claims:** Contains drug dispensed by PZN (package level) – this is mapped to ATC codes and DDDs, day of prescription, day of dispensing, and costs of drugs dispensed from a statutory health insurance perspective without individual deductibles between single sickness funds and pharmaceutical companies. Furthermore, the type of doctor prescribing (e.g. cardiologist, general practitioner) is included.
- **Devices and Aids:** Contains type of device/aid (code and text) (e.g. massage, occupational therapy, walker, wheel chair), quantity prescribed, type of care provider, start and end date, and costs of device/aids.
- **Incapacity to Work and Sick Leave Payments:** This includes ICD-10-GM diagnoses that cause sick leave, duration of sick leave, and the corresponding start and end date of sick leave. In addition, the type of physician that filled-out the sick leave (e.g., cardiologist, general practitioner) and the cost of sick leave payments are incorporated.

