9.7.1.2 Primary and secondary objectives

The incidence rate and corresponding confidence intervals of the primary and secondary endpoints will be estimated as the number of events per 100 person years (% per year). Cox proportional hazard regression will be used to estimate unadjusted and adjusted hazard ratios (multivariate adjusted as well as 1:1 propensity matched). For all models, hazard ratios (HRs), 95% confidence intervals (CIs) and all other regression coefficients will be reported.

Kaplan-Meier curves will be generated to evaluate the time-to-first event associated with the initial treatment.

Rivaroxaban will be compared to Phenprocoumon. Hence, Phenprocoumon will be the reference category in the analysis. A subset of the variables depicted in Table 2 which were selected on an empirical basis, will be included as covariates in the Cox proportional hazards model.

Propensity Score Matching

In this study, we will additionally use propensity score matching. The propensity score will be calculated as the predicted probability of exposure (i.e. probably of receiving Rivaroxaban), given all that is known about a patient (i.e. patient characteristics and covariates).

The probability itself will be derived from a multivariate logistic regression using the parameters thought to act as confounding variables. The propensity score act as a “balancing score” in that all factors that contribute to the score are expected to be independent between treatment groups if the patient population is matched on propensity score and a stratified table of patient characteristics is examined. That is, after propensity score matching all other factors included in the score are expected to be balanced between the two treatment groups. This will minimize confounding by observed baseline covariates by removing any potential relationship between cofounders and exposure group.

In this study, we will estimate propensity scores from all measured factors noted above. These factors will be entered into a logistic regression model, with the factors as the independent variables (with no further variable selection) and the treatment as the dependent variable. From the resulting model, we will predict probability of treatment for each patient; this probability of treatment will be each patient’s estimated propensity score.

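### Prior stroke/TIA is adjusted for only as undated history, so confounding by time since the event may remain in the ischemic stroke hazard ratio and the planned balance checks cannot detect it

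*Protocol*

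**What the plan says.** Table 2 (section 9.3.1) has one categorical variable for stroke or TIA during baseline. Hospital diagnoses "within the 365 days before or on the index date will be used assess whether patients suffered from ischemic stroke or TIA", as will verified outpatient diagnoses from the four quarters before the index quarter. On codes: "Ischemic stroke or TIA will be defined using the ICD-10 GM code I63, I64, G45.9 and G45.8".

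The same history appears in other covariates:

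- CHADS2: "A preliminary stroke/TIA will be assigned two points". CHA2DS2-VASc also gives two points. Both use a 12-month window.
- The modified HAS-BLED score gives one point each for a list that includes "hypertension, renal disease, cirrhosis, and stroke, major bleeding event", over the baseline period.
- The Charlson index has a cerebrovascular item (Table 8).
- Table 10 lists I63, I64 and G45 as separate comorbidities.

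Table 2 also has the total number of baseline hospitalizations, without dates.

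Section 9.4 says of the inpatient records: "It also includes the length of stay (date of hospital admission and end of hospital stay". Outpatient diagnoses are known only by quarter.

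Section 9.7.1.2 says "we will estimate propensity scores from all measured factors noted above", and adds that no further variable selection will be made. The Cox model takes an empirically chosen subset of Table 2. Section 9.7 states that there will be no separate SAP.

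**The concern.** Ischemic stroke is the primary effectiveness outcome, and follow-up starts at first dispensing. How recently a patient had a stroke plausibly affects the early risk of another and the choice of drug. A variable covering day 0 to day 365 treats a patient who starts treatment days after discharge like one who starts almost a year later, and matching may pair them.

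The planned diagnostics (overlap plots, c-statistics, standardized mean differences) examine only what is in the model. The history variable can be perfectly balanced while one arm holds more patients who started soon after an event. The matched and the multivariable hazard ratios would share the problem.

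The outcome definition may add to this. Secondary discharge diagnoses count (section 9.3.3), so a readmission that carries forward a recent I63 code could register as a new event soon after index.

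**Working it through.** **Step 1. Does any covariate carry recency?**

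| Covariate | Look-back | Time since event |
|---|---|---|
| Stroke/TIA variable (Table 2) | 365 days / four quarters | no |
| CHADS2, CHA2DS2-VASc | 12 months | no |
| Modified HAS-BLED | baseline period | no |
| Charlson index, cerebrovascular item | 12 months | no |
| I63, I64, G45 (Table 10) | four quarters | no |
| Number of hospitalizations | baseline period | no |

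None does. The data are not the obstacle. Hospital dates exist, and the protocol uses short dated windows elsewhere: 60 days for VTE and for hip or knee replacement (section 9.2.2), and 90 days for interacting drugs (Table 2).

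**Step 2. Which analysis is exposed?** Section 9.2.2 lists prior events as an exclusion for the sensitivity analysis, which implies that the main analysis keeps these patients. The sensitivity text in section 9.7.1.2 says that a separate analysis will include them, which implies that the main analysis does not. Both cannot hold.

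**Step 3. How large could it be?** The plan states no figure on recency, so there is none to reproduce, and every input here is an assumption. With arms matched on the history variable, let p be the share of patients with a history, q1 and q0 the share of those whose event is recent (rivaroxaban, phenprocoumon), A the hazard ratio of an older event versus none, and r that of a recent versus an older event.

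Bias factor = [(1−p) + p·A·(1 + q1(r−1))] / [(1−p) + p·A·(1 + q0(r−1))]

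One case: p = 0.12, A = 2, q1 = 0.30, q0 = 0.45.

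- r = 2: (0.88 + 0.24×1.30)/(0.88 + 0.24×1.45) = 1.192/1.228 = 0.971
- r = 3: (0.88 + 0.24×1.60)/(0.88 + 0.24×1.90) = 1.264/1.336 = 0.946

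A wider grid, p = 0.05 to 0.15, A = 2, r = 2 to 5:

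| Recent share, q1 vs q0 | Bias factor |
|---|---|
| 50% vs 50% | 1.00 |
| 40% vs 50% | 0.99 to 0.93 |
| 30% vs 50% | 0.98 to 0.86 |
| 20% vs 50% | 0.97 to 0.79 |
| 50% vs 30% | 1.02 to 1.16 |

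**Step 4. Compare with sampling error.** Take the ROCKET-AF stroke rates and patient numbers of section 9.5, and assume one person-year each. Events are 17,000×0.0134 + 30,000×0.0126 = 228 + 378 = 606. The standard error of the log hazard ratio is about √(1/228 + 1/378) = 0.084, so the 95% limits lie about 15% below and 18% above the estimate. With 1:1 matching at 17,000 per arm, events are 228 + 214 = 442, the standard error is about 0.095, and the limits are about 17% below and 21% above. (The printed rates of that row give 0.0134/0.0126 = 1.06, not the stated 0.94. Exchanging them gives 214 + 402 = 616 events, so this comparison hardly changes.)

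**The case against.** Several stronger readings are tempting, and the documents do not support them.

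- *Prior stroke enters as a single yes/no variable.* It does not. It also enters three scores and the Charlson index, and Table 10 separates I63, I64 and G45, so type of event is not wholly pooled. Hemiplegia, which may mark stroke sequelae, has weight 2 in both comorbidity indices (Table 8). None of these carries timing.
- *The hazard ratio is confounded.* That needs recency to differ between arms among patients with a history. The documents give no recency data and do not link recency to drug choice. If recency is equal, the factor is exactly 1.00.
- *The bias matches the effect sought.* The planning hazard ratio of 0.94 comes with a stated power of 0.1105, so the study is not built to detect it. A shift of 3 to 5% lies well inside the sampling error of step 4. What remains is that this bias, unlike sampling error, does not shrink with more patients.
- *Other recorded data, such as mobility aids, should be added too.* Section 9.4 names walkers and wheelchairs only as examples of recorded items. Nothing in the documents supports making them part of this point.

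The best defence is the planned prior-event analysis. On either reading, one version excludes patients with a baseline combined-endpoint event, which is a useful check. It is a partial one. It describes a different population. It keeps patients coded only I64, which Table 2 counts as history but Table 6 omits. And it leaves the hospitalization count undated.

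A uniform 12-month history is a common and defensible default, and the protocol states nothing false about it.

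**Conclusion.** The point holds as a risk of residual confounding, not as a demonstrated bias. No propensity-score or Cox covariate carries time since stroke or TIA, the dates to build one are held, the factor list is closed, and the planned diagnostics cannot reveal an imbalance in recency. Size and direction cannot be fixed from the documents; 1.00, and 0.79 to 1.16 under the imbalances tried, rest on assumptions alone.

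The risk applies to any analysis that keeps patients with prior events. If section 9.2.2 governs, that is the main analysis; if the sensitivity text of section 9.7.1.2 governs, it is the separate one. The change is worth making before the analysis because it is cheap and concerns the primary effectiveness outcome.

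**What to change.** 1. In Table 2, split hospital-coded stroke/TIA by time from discharge to index, for example 0–30, 31–90 and 91–365 days, with a further level for outpatient code only.
2. Add a flag for an index date within 30 days after any hospital discharge.
3. Enter both in the propensity score, and in the Cox covariate set irrespective of empirical selection.
4. Report their standardized differences before and after matching in Table 30.
5. Reconcile section 9.2.2 with the sensitivity text of section 9.7.1.2, and state which analysis excludes patients with prior events.

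The cost is four terms in place of one for the stroke/TIA variable, plus the discharge flag: a net four more model terms, small against about 442 matched stroke events under the assumptions of step 4. No new data are needed, and the sample size and power inputs do not change. Some time bands may be sparse and need merging. At the least, time since the last hospital stroke/TIA should be tabulated by arm after matching.

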9.3.2 Exposure

There are two exposures: New use of Rivaroxaban and new use of Phenprocoumon. Exposure will be defined as one or more prescriptions for the target drug (Phenprocoumon or Rivaroxaban). These prescriptions will be identified using the anatomical therapeutic chemical (ATC) and Pharmazentralnummer (PZN) drug codes including dose and package size (listed in the Annex 2, Table 3 and Table 4).

The exposure start date (index date in the index quarter) for each patient will be defined as the dispense date of the first Rivaroxaban or Phenprocoumon prescription.

Exposure time

Time from index date: Days of supply + Days of potential hospitalizations + Gap period (if no prescription immediately follows). Hospitalizations related to outcome measures will be considered as outcome event.

Gap period

A gap period is allowed when treatment is discontinued before censoring the patient for discontinuation. Patients will be considered as being exposed until 30 days after the end of supply.

Days of supply

Since Rivaroxaban is prescribed with a fixed dose, the number of days of supply corresponds to the size of the package, or the number of days until new prescription, if smaller. Assessing the number of days of supply for Phenprocoumon will be different.

Phenprocoumon Days of Supply:

To account for the intra- and interpersonal variability of the Phenprocoumon treatment regime (INR control and potential titration of Phenprocoumon) an empirical DDD (eDDD) based on the observed Phenprocoumon prescription patterns in the HRI database will be calculated.

The Phenprocoumon PZN code will be used to compute the Amount of Active Ingredient (AAI) dispensed to each patient of the Phenprocoumon group for each prescription. A personalized prescribed daily dose (pDDD) representing the daily dose taken during follow-up will be computed for each patient i :

$$pDDD_i = \frac{\sum_{k=1}^{K-1} AAI_{i,k}}{T_i}$$

k : index of the Phenprocoumon prescriptions during follow-up ($k \in \{1, K\}$)

T: number of days between the first and the last prescription during follow-up

The eDDD corresponds to the median of the distribution of the pPDD estimated over all patients who were solely treated with Phenprocoumon during the study period. The Exposure Time (ET) corrected from the intra- and interpersonal variability of Phenprocoumon treatments can be computed for each patient i as:

$$ET_i = \frac{\sum_{k=1}^K AAI_{i,k}}{eDDD}$$

Date of switch

Patients who receive a prescription for an OAC other than the index OAC prescription (including other NOACs) during the follow-up period will be considered as switchers if the new prescription occurred either before the end of supply of the current prescription or within the gap period after the end of supply. The dispense date of the new OAC will be defined as the date of switch and patients will be censored.

Date of discontinuation

Discontinuation will be defined as no follow-up prescription for either Rivaroxaban or Phenprocoumon at the end of the gap period after the end of supply. Patients receiving prescriptions for Rivaroxaban 10 mg will also be considered to have terminated the treatment. The last day of the exposure time will be defined as the date of discontinuation and patients will be censored.

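### Hospital days stay in the denominator of the phenprocoumon daily dose and are then added again to exposure time, which stretches exposure in that arm by an amount the documents do not give

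*Protocol*

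**What the plan says.** All the rules stand in Protocol 9.3.2.

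- **Exposure time, both arms:** "Time from index date: Days of supply + Days of potential hospitalizations + Gap period (if no prescription immediately follows".
- **Gap, both arms:** "Patients will be considered as being exposed until 30 days after the end of supply".
- **Rivaroxaban supply:** "the number of days of supply corresponds to the size of the package, or the number of days until new prescription, if smaller". No daily dose is estimated.
- **Phenprocoumon supply:** "A personalized prescribed daily dose (pDDD) representing the daily dose taken during follow-up will be computed for each patient". It is the drug dispensed at prescriptions 1 to K−1 divided by T, the "number of days between the first and the last prescription during follow-up". Then "The eDDD corresponds to the median of the distribution of the pPDD estimated over all patients who were solely treated with Phenprocoumon". Under the same heading, *Phenprocoumon Days of Supply*, the protocol continues: "The Exposure Time (ET) corrected from the intra- and interpersonal variability of Phenprocoumon treatments can be computed for each patient". The formula is total dispensed drug over all K prescriptions divided by eDDD.
- **Use of the result:** "The last day of the exposure time will be defined as the date of discontinuation and patients will be censored".

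Section 9.4 states that dates of admission and end of stay are held. Section 9.7 says there will be no separate SAP, so 9.3.2 is the place where this rule is fixed.

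**The concern.** The two rules rest on opposite premises. Adding hospital days to supply makes sense only if outpatient tablets are not consumed in hospital. Dividing dispensed drug by all calendar days between prescriptions makes sense only if they are. Used together, they let hospital time lengthen phenprocoumon exposure twice: once through a lower eDDD, and once by direct addition.

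Rivaroxaban has no estimated dose and so lacks the first route. The last day of exposure is the censoring date, so in one arm of a comparative study some time after supply has ended would be counted as exposed. Events in that time would be attributed to phenprocoumon.

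**Working it through.** The protocol states no figure for eDDD, hospital days or exposure time, so there is nothing of its own to reproduce here. The formulas are from 9.3.2; inputs marked *assumed* are not in the documents.

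**1. Algebra.** Let d be the true outpatient daily dose and H the hospital days within T. On the protocol's premise that outpatient supply is not used in hospital, the drug used over T is d(T−H). Then

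- pDDD = d(T−H)/T
- if all patients are alike, eDDD = d(T−H)/T, and supply over T = d(T−H)/eDDD = T
- adding hospital days gives T + H, although only T days have passed

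For T = 365 and *assumed* H of 5 or 12:

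| H | eDDD/d | Supply as written | Plus H | Correct | Excess | Supply stretch |
|---|---|---|---|---|---|---|
| 5 | 360/365 = 0.986 | 365 | 370 | 365 | 5 | 365/360 − 1 = 1.4% |
| 12 | 353/365 = 0.967 | 365 | 377 | 365 | 12 | 365/353 − 1 = 3.4% |

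With H removed from T, eDDD = d, supply is 360 or 353, adding H gives 365, and the excess is 0.

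**2. Patients who differ.** eDDD is a cohort median, so a patient's own stay barely changes that patient's own supply. Two simulations of 200,000 patients with log-normal doses (all inputs *assumed*) gave:

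- 0.8 stays per year, averaging 5, 8 or 12 hospital days per patient-year: supply 1.4%, 2.3% or 3.5% too long, or 5.0, 8.4 or 12.6 days per year.
- 20–60% of patients admitted, mean 7–21 hospital days each, T of 120–700 days: supply 0.5–4.2% too long, about 2–18 days per patient. Never-admitted patients gained about 2–19 days.

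**3. Cumulative or per prescription.** The ET formula sums all K prescriptions, so the stretch builds up: 5–13 days per year. The switch and discontinuation rules look instead to the end of supply, for switching explicitly that of the current prescription. Read that way, only the last pack's stretch counts. With packs lasting 50–150 days (*assumed*), that is 50 × 1.4% = 0.7 to 150 × 3.5% = 5.3 days.

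**4. Rivaroxaban.** Pack of 98, 7 hospital days, refill on day 105: 98 + 7 = 105, excess 0. Refill on day 90: the capped interval of 90 may already contain the stay, and 90 + 7 = 97, but that is below 98 + 7 = 105. Exposure before the gap is never pushed beyond pack size plus hospital days.

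**5. Effect on a rate.** *Assume* one year of treatment, half the patients ending by discontinuation, x extra days, and an untreated event rate k times the treated rate. The ratio of the phenprocoumon rate with the stretch to the rate without it is

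[(365 + 0.5(30+x)k)/(365 + 0.5(30+x))] ÷ [(365 + 15k)/(365 + 15)]

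- Cumulative: x = 5, k = 1.5 gives 1.0229/1.0197, or +0.3%; x = 12.6, k = 3 gives 1.1103/1.0789, or +2.9%.
- Per prescription: x = 0.7, k = 1.5 gives +0.04%; x = 5.25, k = 3 gives 1.0921/1.0789, or +1.2%.
- For any k below 1 the ratio falls below 1.

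**6. Scale.** With the sizes and the Rocket-AF stroke rates printed in 9.5, over one year: 17,000 × 0.0134 = 228 and 30,000 × 0.0126 = 378 events. The standard error of the log hazard ratio is √(1/228 + 1/378) = 0.084, and 1.96 × 0.084 = 0.16.

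**The case against.** **The formula's label.** The strongest reply is that total drug over eDDD is labelled Exposure Time, not days of supply. If it is the whole exposure time, hospital days are never added again and nothing is counted twice. That reading is open. But the formula stands under the phenprocoumon supply heading, the reading contradicts the general definition in the same section, and it would drop the 30-day gap for phenprocoumon as well. The text needs correcting on either reading.

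**Use of tablets in hospital.** The premise that outpatient tablets are not used in hospital is implied, not stated. If they are used, T is right and the added hospital days are the error, in both arms. The two rules still cannot both be right.

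**Materiality.** Every input to the size is assumed, and even the largest shift computed (2.9%) is well inside the sampling error in step 6. This stands, and it makes the point minor.

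**Stronger readings the documents do not support.** A reader might infer that the rule favours rivaroxaban on both primary endpoints. Those endpoints are ischemic stroke and ICH. A k above 1 is plausible for thromboembolic events, but section 7 names bleeding as a risk of VKA treatment, so untreated time would more likely dilute the phenprocoumon ICH rate. The cerebral-benefit composite would be pulled both ways. A reader might also infer that each admitted patient's own stay is counted twice for that patient. It is not: the stretch works through the cohort median and reaches all phenprocoumon patients.

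**Conclusion.** The point holds as an inconsistency in the definition of exposure, with a small effect. Read with the general definition, 9.3.2 lets hospital time lower eDDD, lengthens every phenprocoumon supply, and then adds hospital days again. Some time after phenprocoumon supply has ended is counted as exposed, and the censoring date moves later in that arm only.

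The size depends on two things the documents do not settle: the amount of hospital time, and whether supply is judged cumulatively or per prescription. On the assumptions above the stretch is a few percent of supply, which is less than the 30-day gap per year of treatment. The phenprocoumon rate would be expected to rise for ischemic stroke and the thromboembolic endpoints and more likely to fall for ICH. No overall direction of bias should be claimed.

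**What to change.** In 9.3.2, define T in the daily-dose formula as the days between first and last prescription minus the hospital days in that interval. State that total drug divided by eDDD is days of supply, to which hospital days are added once and then the gap, as for rivaroxaban. Say also whether the end of supply is judged cumulatively or for the current prescription.

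An alternative is to keep T as calendar days and not add hospital days again for phenprocoumon. This removes the double count, but it spreads hospital time over all patients through the median and leaves the two arms under different rules.

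Either change is a line or two of text. The dates needed are already in the database (9.4), so no further data are required.
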